1. SYNOPSIS

Study Title	The development and pilot testing of a new Magnetic Resonance (MR) imaging					
	protocol to quantify both myeloma disease burden and associated bone loss					
Internal ref. no. / short title	LOOMIS- myeLOma bOne MrI Study					
Study Design	Observational Prospective Cohort					
Study Participants	Group 1- Myeloma					
	Group 2- Monoclonal Gammopathy of Unco	ertain Significance (MGUS)				
	Group 3- Healthy Volunteers					
Planned Sample Size	60					
	Group 1- Myeloma- 34					
	Group 2- MGUS - 13					
	Group 3 - Healthy Volunteers - 13					
Planned Study Period	September 2017 – December 2021					
	Objectives	Outcome Measures				
Primary	To develop and pilot test a novel	Novel imaging based endpoints:				
	Magnetic Resonance (MR) imaging	1. DW-MRI (Diffusion Weighted-				
	protocol with the aim to accurately: 1. Quantify tumour burden	Magnetic Resonance Imaging): ADO (apparent diffusion coefficient)				
	2. Quantify bone loss	change (Pawlyn et al , 2016)				
	2. Quantity bone loss	2. Total spinal 'hole' volume				
		3. Total spine 'collapse' volume				
		4. FSA (Fine Structural Analysis):				
		trabecular wall thickness (Rafferty				
		et al, 2016)				
		Correlate endpoints:				
		Bone density (DXA imaging)Serum CTX-1				
		Serum P1NP				
		Further experimental serum				
		biomarkers of myeloma				
	bone disease					
Secondary	To pilot test a novel MR imaging protocol with the aim to accurately:	1 and 2 - Repeat quantification of endpoint parameters after induction				
	Detect longitudinal changes in	therapy and best response achieved				
	tumour load with therapy	by IWMG criteria or at treatment				
	2. Detect longitudinal changes in	failure				
	bone microarchitecture with					
	therapy					
	3. Assess participants Quality of					
	Life (EQ-5D) throughout the					
	study					

4.	Assess participants experience of	3 – Analyse participants quality of
	the novel MR imaging scan	life using data from the EQ-5D-5L
		questionnaire
		4- Analyse participants experience
		of the novel MR imaging using data
		from MRI/DXA scanning
		questionnaire

2. ABBREVIATIONS

	,
ADC	Apparent Diffusion Coefficient
CI	Chief Investigator
CRF	Case Report Form
DWI	Diffusion Weighted Imaging
DWMRI	Diffusion Weighted Magnetic Resonance Imaging
DXA	Dual-energy X-ray Absorptiometry
FSA	Fine Structure Analysis
GCP	Good Clinical Practice
GP	General Practitioner
ICF	Informed Consent Form
ICH	International Conference of Harmonisation
IMWG	International Myeloma Working Group
MGUS	Monoclonal Gammopathy Of Uncertain Significance
MR	Magnetic Resonance
MRI	Magnetic Resonance Imaging
NHS	National Health Service
NOC	Nuffield Orthopaedic Centre
NRES	National Research Ethics Service
PET-CT	Positron Emission Tomography-Computed Tomography
PI	Principal Investigator
PIL	Participant/Patient Information Leaflet
R&D	NHS Trust R&D Department
REC	Research Ethics Committee

SOP	Standard Operating Procedure
SRE	Skeletal Related Events
WBLDCT	Whole-body low dose Computed Tomography
sFLC	Serum free light chains

3. BACKGROUND AND RATIONALE

Multiple myeloma, a malignancy of monoclonal B-cells, is the second most common haematological malignancy, compromising of 2% of all cancers in the UK and is currently incurable. At diagnosis and each relapse, treatment of myeloma consists of conventional chemotherapy combined with novel agents. In those fit enough, autologous (and in some cases allogeneic) stem cell transplantation is used to prolong remissions (NICE, 2016). A number of tests are used for disease quantification to guide therapy; however these tests each have limiting factors. Bone marrow histology using a bone marrow biopsy is painful and invasive; it also cannot predict global myeloma infiltration, which is not uniform and varies through the skeleton, and no bone loss information can be obtained. Serum paraprotein, light or heavy chain quantification must be used for regular monitoring; however this fails in non-paraprotein secreting myelomas, and although it tracks the secretory capacity of a plasma cell clone, that feature can change over the course of the disease.

PET-CT (positron emission tomography- computed tomography) is the imaging gold standard in myeloma for quantifying total disease burden (Cavo *et al*, 2017). This cannot however quantify bone loss, either microarchitecture changes or lytic lesions. It therefore cannot be used to track response to anti-bone-resorptive therapies.

There are a number of widely used modalities that are currently available to visualise bone destruction; including conventional MR (magnetic resonance), whole body low dose CT (WBLDCT) (Pianko *et al*, 2014) and X-ray skeletal survey. However, none of these techniques are quantitative (Marti-Bonmati *et al*, 2015). Of particular note, high-resolution bone volume quantifying CT techniques cannot be used on the central skeleton due to high radiation exposure; although trialled on cortical bone in the peripheral skeleton (Farr *et al*, 2013), this is not the usual site of myeloma bone loss. DXA (Dual-energy X-ray Absorptiometry) scans are widely used in the UK for assessing bone density in patients with osteoporosis but are an insensitive tool in myeloma as it does not show fractures (Marti-Bonmati *et al*, 2015), and therefore are not routinely commissioned for imaging myeloma patients. All of these imaging modalities require significant time and resource commitment over a typical myeloma disease course. Typically a patient may require X rays, PET-CT and spinal MRI within a few weeks for complete staging. If there were a single imaging method that could provide all required quantified staging information this would have both economic and patient convenience benefits.

The use of Magnetic Resonance Imaging (MRI) in Multiple Myeloma has increased dramatically over the last 10 years (Derlin & Bannas, 2014). MRI offers improved detection of lesions in the spine, pelvis, sternum, skull and scapulae as well as exceptional depiction of the spinal cord and nerve roots, detection of soft tissue manifestations and the ability to differentiate between physiological and myeloma-infiltrated bone marrow. Several studies have shown that asymptomatic patients with detectable lesions on MRI have a higher probability to become symptomatic earlier than patients without such lesions. This has therefore been incorporated in the revised IMWG diagnostic criteria (Rajkumar *et al*, 2014).

In addition to morphological MRI, there are newer functional MR techniques such as diffusion-weighted imaging (DWI). However there is limited published data for DWI (Diffusion Weighted Imaging) in the context of initial staging. A recent study has shown that diffusion-weighted imaging not only allows for detection of myeloma manifestations such as lytic lesions (DW-MRI was found superior to the whole-body x-ray for the detection of bone involvement in 20 patients with relapsed, refractory myeloma in all

areas of the skeleton except the skull), but also that the DWMRI-generated apparent diffusion coefficient (ADC) significantly differs before and after initiation of therapy, so allowing calculation of change in disease burden (Giles *et al*, 2015). DW-MRI uses ADC measurement to quantify disease and is influenced by tissue microarchitecture. The speed, quantitative capabilities and superior sensitivity compared with conventional MRI sequences have led to the adoption of DW-MRI at several leading myeloma centres worldwide. ADC measurements are not without challenges, as they can be influenced by scanner manufacturer and field strength, however are perceived to be less susceptible to equipment and physiological influences than PET-CT. In a recent trial (Pawlyn *et al*, 2016), DW-MRI scans were compared with FDG (f-fluorodeoxyglucose) PET-CT and found to detect a statistically significant higher burden of myeloma disease. Investigations into the patient experience of DW-MRI have suggested that the DW-MR imaging technique is acceptable to patients as 86% found the overall experience acceptable. It is therefore proposed to be a novel non-ionising radiation imaging modality for quantitative assessment of disease burden and therapy response (Latifoltojar *et al*, 2017; Pawlyn *et al*, 2016). Importantly however, DW MRI cannot measure bone density.

The extent of lytic bone disease, the major cause of morbidity in myeloma affecting over 90% of patients, still cannot be quantified. Lytic lesions as seen on X-rays take many years to heal. In MGUS (Monoclonal gammopathy of uncertain significance); a precursor of multiple myeloma without any signs of the malignant disease (Bauerle *et al*, 2009); it is suspected that early bone destruction is associated with transformation to malignancy, but no appropriate imaging modality exists to assess or monitor this, meaning this patient cohort may be missing out on disease modifying therapies. We wish to address this important unmet clinical need by piloting a novel MR imaging assessment of disease burden and bone loss in myeloma. Farr et al using peripheral qCT have shown MGUS patients have early bone loss (Farr *et al*, 2013). This has been subsequently termed as monoclonal gammopthay of skeletal significance, MGSS (Drake, 2014).

On to the state of the art DW-MRI technique of quantifying disease burden, we propose to add 2 further experimental MR components to quantify myeloma bone loss, which can take the form of a) lytic lesions (holes), b) vertebral collapse and c) trabecular thinning. We will address this in the following way:

- 1. High resolution 3D imaging of spine and pelvis: 'hole' and 'collapse' volumes will be quantified. This is entirely novel and will be produced by OCMR scientists.
- 2. Fine SA: Osteotronix' *fine*SA* (FSA) technology is able to extract microstructural information from MRI data sets acquired on a standard clinical MRI scanner. In this study, we are particularly interested in using the FineSA metric as a correlate of trabecular wall thickness, to indicate bone remodelling. The FSA metric has been shown to correlate tightly with gold standard bone density measurements in rats (Evans *et al*, 2014) and human cadaveric spine specimens (Rafferty *et al*, 2016). The only other means to measure these parameters is by computed tomography, not feasible in the human body in vivo due to the high radiation dose that would result from microstructural CT of central bones. FSA will be performed at two sites in the lumbar spine, and repeated on each patient (within the same appointment) to assess reproducibility. Further central skeleton sites may be added with technique development.

We therefore aim to develop and pilot a MR imaging protocol and assess its ability to achieve the following: quantification of tumour burden and bone loss, detecting longitudinal changes in tumour load

with therapy and detecting longitudinal changes in microarchitecture with therapy. We also aim to investigate sensitivity of the different imaging techniques in detection of bone loss. This will be investigated by correlating the DXA imaging data (accepted imaging for measuring longitudinal changes in bone density) with our experimental protocol, to see if it is possible to achieve quantifiable data of bone density.

We hypothesize that this imaging tool will be superior to the combined current standard-of-care investigations in the quantification of tumour burden and bone loss. There are currently no tools available for quantifying structural changes to bone and overall bone loss in myeloma. To our knowledge, this has never been done before; if shown to be feasible, such a method would have two important applications: to precisely guide commissioned therapies in the clinic, so improving patient management; and as an exciting, novel research tool for the longitudinal combined assessment of tumour burden and cancer-induced bone disease in response to therapy.

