4. OBJECTIVES AND OUTCOME MEASURES/ENDPOINTS

	Objectives	Outcome Measures
Primary	To develop and pilot test a novel MR imaging protocol with the aim to accurately: 1. Quantify tumour burden 2. Quantify bone loss	Novel imaging based endpoints: 1. DW-MRI: ADC change (Pawlyn et al, 2016) 2. Total spinal 'hole' volume 3. Total spine 'collapse' volume 4. FSA: trabecular wall thickness (Rafferty et al, 2016) Correlate endpoints: Bone density (DXA imaging) Serum CTX-1 Serum P1NP Further experimental serum biomarkers of myeloma bone disease
Secondary	To pilot test a novel MR imaging protocol with the aim to accurately: 1. Detect longitudinal changes in tumour load with therapy 2. Detect longitudinal changes in bone	1 and 2 - Repeat quantification of endpoint parameters after induction therapy and best response achieved by IWMG criteria or at treatment failure

microarchitecture with	3 – Analyse participants quality of
therapy	life using data from the EQ-5D-5L
3. Assess participants	questionnaire
Quality of Life (EQ-5D)	
throughout the study	
4. Assess participants experience of the novel MR imaging scan	4- Analyse participants experience of the novel MR imaging using data from MRI/DXA scanning questionnaire

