- 3. Experimental MR imaging protocol (1 hour radiology appointment). MRI scans will be performed in a 60-minute protocol on the 1.5T or 3T Avanto MRI scanner (Siemens, Germany) installed at OCMR (Oxford Centre for Magnetic Resonance), John Radcliffe Hospital, [name]. Scans will include: localizer images, high-resolution 3D imaging of the pelvis and lumbar spine, diffusion-weighted MRI imaging following the method described for use in myeloma patients by Giles *et al* (Giles *et al*, 2015; Giles *et al*, 2014; Pawlyn *et al*, 2016), and an experimental bone density quantification MR method based on published techniques (Evans *et al*, 2014; Rafferty *et al*, 2016), using software from Osteotronix Ltd, in the pelvis and two sites in the lumbar spine. Blinded data gathered from experimental MRs will be used to generate disease burden in percentage marrow infiltration, high-resolution 3D imaging-generated total spinal lytic and collapse volumes, and bone structure quantification. Marrow infiltration will be correlated with marrow infiltration data as determined by bone marrow biopsy (and PET-CT scans where performed). MR-generated bone density quantification and total spinal lytic and collapse volumes will be correlated with bone mineral density as estimated by DXA scan. As there is no

accepted "gold standard" method for quantifying myeloma-associated bone loss against which to compare, in all the healthy volunteers and in 10 myeloma patients who are tolerating the procedure without problem and who are willing repeat MR bone density measurements will be performed (a subsection of the whole protocol, lasting max. 15 minutes) within each attendance, to assess reproducibility.

4. At the end of both the experimental MR and the DXA scan, all participants will be asked to complete the Quality of Life Questionnaire and the novel MR experience questionnaire. This assessment will take approximately 15 minutes.

See Appendix A for time frame of assessments.

No contrast medium will be used.

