10.2. Analysis of Outcome Measures/Endpoints

Differences in baseline characteristics between participants groups (1, 2 and 3) will be compared using chisquare test for categorical variables and one-way analysis of variance (ANOVA) for continuous variables.

To assess ability of MRI to detect improvement or deterioration in tumour burden and bone health, differences between DW-MRI data imaging from the two time-points (baseline and 6 months follow up) will be tested using paired t test. In addition, ADC, total spine 'hole' and 'collapse' volume and FSA trabecular wall thickness will be compared with bone mineral density at the lumbar spine, total hip and femoral neck T score and g/cm², serum CTX-1 and PINP using correlation analysis in group 1 (complete/very good partial response vs. partial response) and in group 2. These models will be run at baseline and at follow-up.

Differences between groups 1 and 2 in experimental MR measurements at follow up will be estimated using one-way analysis of variance (ANOVA) and analysis of covariance (ANCOVA) when baseline values and potential confounders (including gender, age and body mass index (BMI)) are adjusted. Endpoints will be checked for normality and transformed if possible.

In order to determine the change in EQ-5D throughout the study, repeated measured linear regression analysis will be used where EQ-5D at baseline and follow up will be included as outcome and group as exposure.

Finally, a descriptive analysis of the novel MR imaging scan questionnaire will be conducted to understand participant's experience with the new technique.

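### The only planned link between MR and DXA or bone markers is a correlation at each visit, which cannot show that change in MR tracks change in bone

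*Combined protocol and SAP*

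**What the plan says.** Section 3 sets the aim, "We also aim to investigate sensitivity of the different imaging techniques in detection of bone loss", and gives the method: "This will be investigated by correlating the DXA imaging data (accepted imaging for measuring longitudinal changes in bone density) with our experimental protocol". It ends that sentence with a narrower purpose, namely whether bone density can be quantified from MR at all.

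The objectives table in Section 4 lists longitudinal change in bone microarchitecture with therapy as a secondary objective, measured by "Repeat quantification of endpoint parameters after induction therapy and best response achieved by IWMG criteria or at treatment failure". Section 5 repeats MR, DXA and the bone markers in Groups 1 and 2 at six months, or sooner at progression, in order to evaluate change in disease burden and bone loss.

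For analysis, Section 7.4 says "MR-generated bone density quantification and total spinal lytic and collapse volumes will be correlated with bone mineral density as estimated by DXA scan". Section 10.2 correlates ADC, hole volume, collapse volume and FSA with BMD, CTX-1 and P1NP within Group 1 (by response category) and within Group 2, and adds "These models will be run at baseline and at follow-up".

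Two other analyses in 10.2 use follow-up MR data. One is a paired t test between the two visits, worded for DW-MRI data. The other is an ANOVA/ANCOVA comparing Groups 1 and 2 on MR measures at follow-up, with baseline adjustment. Neither involves DXA or markers.

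**The concern.** The study collects MR, DXA and turnover markers twice in the same patients, and part of its purpose is to learn whether MR can follow bone over time. The external check on MR uses each visit separately. A correlation of levels is dominated by who has strong bone and who has weak bone, and this differs little between visits. Whether the two measures move together in one patient is a different question, and 10.2 does not ask it.

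The risk lies in interpretation. Similar, fairly strong correlations at baseline and follow-up could be reported as support for using MR to monitor bone when they carry almost no information on that. The paired data that do carry such information would have no planned use for this purpose.

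**Working it through.** **The plan's own figure.** The only sample-size calculation (10.1) is for ADC: difference 0.75, SD 0.5, ratio 0.15, 80% power, alpha 0.05 (two-sided assumed). Larger group: (1.96 + 0.84)² × 0.5² × (1 + 1/0.15) / 0.75² = 26.7, so 27. Smaller group: 0.15 × 27 = 4.05, so 5. The total is 32, against 34 (29 vs 5) stated; power at 29 vs 5 is about 85%. No bone endpoint enters, so the calculation matters here only for the numbers available: 34 in Group 1 and 13 in Group 2.

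The documents give no variance, change or correlation for FSA or DXA. Everything below is therefore illustration under stated assumptions.

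**Step 1. Levels can agree when changes do not.** Let each measure be a stable personal component shared by MR and DXA (variance 0.8) plus independent visit-level variation (variance 0.2).

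- Correlation at either visit = 0.8 / (0.8 + 0.2) = 0.80.
- In the change score the stable part cancels and only independent terms remain, so the correlation of changes = 0.

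If the stable parts correlate at 0.7 or 0.5 instead of 1, the visit correlations are 0.7 × 0.8 = 0.56 or 0.5 × 0.8 = 0.40. The change correlation is still 0.

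**Step 2. Adding real change.** Let the levels have SD 1 and baseline correlation 0.70. Let the changes have SD s in both measures, correlation c with each other, and be independent of baseline. Then

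follow-up r = (0.70 + c·s²) / (1 + s²).

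| s | c = 0 (no tracking) | c = 0.8 (good tracking) |
|---|---|---|
| 0.1 | 0.69 | 0.70 |
| 0.2 | 0.67 | 0.70 |
| 0.3 | 0.64 | 0.71 |
| 0.5 | 0.56 | 0.72 |

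Up to s = 0.3 the two columns differ by at most 0.708 − 0.642 = 0.07. By Fisher's z, a correlation of 0.70 at n = 34 has 95% limits tanh(0.867 ± 1.96/√31), that is 0.47 to 0.84. Even the gap of 0.16 at s = 0.5 lies within that range.

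**Step 3. Mean change is invisible to a correlation.** Take s = 0.3, c = 0 and a mean DXA change of −0.2. A mean MR change of 0 or of −0.5 gives the same visit correlations, 0.70 and 0.64. Visit correlations therefore also say nothing about which technique registers more change.

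**Step 4. What a change-score correlation would deliver.** For r = 0.5, atanh(0.5) = 0.549.

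- n = 34: tanh(0.549 ± 1.96/√31) = 0.19 to 0.72
- n = 13: tanh(0.549 ± 1.96/√10) = −0.07 to 0.82
- n = 5 (the expected partial-response subgroup): tanh(0.549 ± 1.96/√2) = −0.68 to 0.96

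The smallest correlation detectable with 80% power, tanh(2.80/√(n − 3)), is 0.46 at n = 34 and 0.71 at n = 13.

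**The case against.** **The plan does contain longitudinal analyses.** The paired t test is introduced as assessing MRI's ability to detect change in tumour burden and bone health. The heading of 8.1 uses the diffusion-weighted label for the whole MR session, so the test may be meant to include FSA and the volumes. This stands in part: it would be wrong to infer that the plan has no analysis of change. But the wording names DW-MRI data, and Section 3 says DW-MRI cannot measure bone density. Even on the broad reading, the test shows that an MR measure moved, not that it moved with bone. The same limit applies to the ANCOVA.

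**The sensitivity aim is narrower than it looks.** The sentence does not say over time, and its stated purpose is whether bone density can be quantified. Visit-wise correlation suits that question. This stands, and those correlations should stay. The longitudinal need comes from the secondary objective and from the reason given in Section 5 for repeating the scans.

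**Superiority.** A reader might infer that the plan sets out to show MR more sensitive than DXA and that the correlations defeat this. The documents do not support that. The hypothesis is "We hypothesize that this imaging tool will be superior to the combined current standard-of-care investigations in the quantification of tumour burden and bone loss", while Sections 3 and 7 place DXA outside routine myeloma care. Nor would a high correlation with DXA count against MR: DXA scans "are an insensitive tool in myeloma as it does not show fractures", a remark about fractures rather than density.

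**A head-to-head comparison of responsiveness.** Comparing mean change over SD of change for FSA and BMD is tempting. Section 7.4 acknowledges that there is no gold standard, and the groups mix new, relapsed, smouldering and MGUS patients whose bone may change in opposite directions. A larger standardised change would not establish better detection of bone loss.

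**It is a pilot powered on ADC.** True, and this is why the addition should be labelled exploratory.

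**Conclusion.** The concern holds in a limited form. The visit-wise correlations are adequate for concurrent validity but cannot show that MR change tracks change in BMD or turnover markers, and no other planned analysis does so. Under the assumptions above, follow-up correlations of 0.56 to 0.69 with no tracking and 0.70 to 0.72 with good tracking could not be told apart at n = 34. The 0.80, 0.80 and 0 example makes the same point, but it contains no true bone change and describes a general property rather than this trial.

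The conclusion itself does not depend on those values. It follows from 10.2 containing no analysis that pairs MR change with DXA or marker change. It is a gap between purpose and analysis in a pilot, not a numerical error, and it does not touch the ADC comparison.

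**What to change.** In 10.2:

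- Add the correlation of within-patient change in FSA, hole volume and collapse volume with change in lumbar spine BMD, CTX-1 and P1NP, with 95% CIs. Report it separately for Group 1 and Group 2 and label it exploratory. Do not rely on a partial-response subgroup of about five.
- State that the paired baseline-to-follow-up comparison covers FSA, hole volume and collapse volume as well as the DW-MRI data, and report the DXA change beside it descriptively.
- Say that the visit-wise correlations address concurrent validity and will not be interpreted as evidence of monitoring ability or of superior sensitivity.

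The cost is a few sentences and some extra estimates from data already collected under 7.5. The drawback is imprecision, as in Step 4: the results can guide a later study but cannot settle the question.
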